4.2. Scientific Rationale for Study Design

Blinding, Control, Study Phase/Periods, Intervention Groups

Blinded treatment for guselkumab and placebo will be used to reduce potential bias during data collection and evaluation of endpoints. A placebo control will be used to establish the frequency and magnitude of changes in clinical endpoints that may occur in the absence of active treatment. Randomization will be used to minimize bias in the assignment of participants to treatment groups, to increase the likelihood that known and unknown participant attributes (eg, demographic and baseline characteristics) are evenly balanced across treatment groups, and to enhance the validity of statistical comparisons across treatment groups.

4.2.1. Study-Specific Ethical Design Considerations

Potential participants will be fully informed of the risks and requirements of the study and, during the study, participants will be given any new information that may affect their decision to continue participation. They will be told that their consent to participate in the study is voluntary and may be withdrawn at any time with no reason given and without penalty or loss of benefits to which they would otherwise be entitled. Only participants who are fully able to understand the risks, benefits, and potential adverse events (AEs) of the study and provide their consent voluntarily will be enrolled.

The total blood volume to be collected from each participant in each group (181.5 mL over approximately 48 weeks) is far less than the American Red Cross standard limit for whole blood donation (approximately 475 mL q8w) and is therefore considered an acceptable amount of blood to be collected over this time period. For more details regarding blood collection, see Blood Sample Collection in Section 8.

4.3. Justification for Dose

The following guselkumab dose regimens are selected for this Phase 2 POC study in participants with moderate to severe HS:

- Guselkumab 1200 mg IV at Weeks 0, 4, and 8, followed by 200 mg SC q4w through Week 36
- Guselkumab 200 mg SC q4w from Week 0 through Week 36
- Placebo IV and SC administration through Week 16. At Week 16, participants in the placebo group will cross over to:
 - Guselkumab 200 mg SC (q4w from Week 16 to Week 36), or
 - Guselkumab 100 mg SC (Weeks 16, 20, 28 and 36; placebo SC at Weeks 24 and 32).

These guselkumab dose regimens were selected based on existing safety information from relevant preclinical and clinical studies, the approved dose regimen for psoriasis, and the objective of determining the maximum efficacy of guselkumab possible for treatment of HS. Published information about adalimumab (an anti-TNF α monoclonal antibody) on relative dosing requirements among Crohn's disease, psoriasis, and HS patients also contributed to the choice of these dose regimens, along with data from an open-label HS clinical trial using ustekinumab (an anti-IL-12/IL-23 monoclonal antibody). 1,2,17,18,19

This is a POC study, therefore, the maximum feasible dose (1200 mg IV), based on safety margins from preclinical and clinical studies, is being evaluated to define the maximum efficacy of guselkumab possible in HS. Single IV doses of guselkumab as high as 10 mg/kg, with the highest IV single dose tested being 987 mg, have been previously studied in a Phase 1 plaque psoriasis study. Additionally, guselkumab IV doses of up to 50 mg/kg weekly for 5 weeks, and guselkumab SC doses of up to 50 mg/kg weekly for 24 weeks, were well tolerated in cynomolgus monkeys (Section 2.2). These data support an acceptable exposure margin between

the predicted guselkumab exposures at the proposed dose regimens compared to those observed in toxicology studies; the estimated safety margins are approximately 4-to-6-fold for the 1200 mg IV dosing (See Appendix 8 [Section 10.8]). Of note, the 1200 mg IV dose is the same as the high guselkumab dose to be studied in Crohn's disease (NCT01369355, ClinicalTrials.gov). The 1200 mg IV dose regimen will help assess if incremental HS efficacy is possible with guselkumab exposure exceeding what can be practicably achieved with SC dosing.

A guselkumab 200 mg SC q4w dose, approximately 4-fold of the approved psoriasis dose (ie, 100 mg SC at Weeks 0 and 4, then 100 mg SC q8w thereafter), is also included in this POC study to determine the HS efficacy resulting from the maximally practicable SC dose of guselkumab.

Participants randomized to placebo will cross over to blinded guselkumab treatment at Week 16, including the 200 mg SC q4w dose and a lower 100 mg SC dose at Weeks 16 and 20, followed by q8w through Week 36, which is the approved psoriasis dose. Based on the results from an open-label ustekinumab HS study, it is likely that the psoriasis dose regimen could provide some clinical benefits. Comparison of the relative efficacy of these two dose groups will provide useful data for determining if a dose higher than the optimal psoriasis dose provides incremental efficacy in HS.

Available preclinical observations and clinical data from other therapies suggest that a dose higher than the psoriasis dose may be needed in HS to achieve optimal efficacy. For example, IL-17+ CD4 T cells were shown to be enriched more than 40-fold in HS-involved skin compared with normal skin, ¹¹ while the ratio was only approximately 2-fold for psoriasis. ⁶ IL-17A gene expression and protein levels have been reported to be highly up-regulated in HS affected skin compared to unaffected skin. ⁷ Additionally, studies have shown similar IL-23/Th17 pathway gene expression in HS- and Crohn's disease-affected tissues, indicating potential commonality in the pathophysiology of these autoinflammatory conditions. ^{16,22} Moreover, an adalimumab Phase 2 dose-ranging HS study found that an adalimumab dosage comparable with that used for Crohn's disease and ulcerative colitis, and essentially twice the psoriasis dose, provided better efficacy compared with the approved psoriasis dose, ⁸ and ultimately became the adalimumab dose approved for HS treatment. Finally, HS patients are generally heavier than patients with psoriasis (median body weight of approximately 94 kg and 89 kg, respectively)^{12,14} and guselkumab exposure has been shown to be lower in heavier participants.

4.4. End of Study Definition

A participant will be considered to have completed the study if he or she has completed all scheduled study interventions through Week 36 and has completed all assessments at Week 48 of the safety follow-up period.

The end of study is considered as the last visit for the last participant in the study. The final data from the study-site will be sent to the sponsor (or designee) after completion of the final participant assessment at that study-site, in the time frame specified in the clinical trial agreement.

5. STUDY POPULATION

A target of 180 participants will be enrolled under the CNTO1959HDS2001 protocol.

Screening for eligible participants will be performed within 4 weeks before administration of the study intervention. Refer to Section 5.4, Screen Failures for conditions under which the repeat of any screening procedures is allowed.

The inclusion and exclusion criteria for enrolling participants in this study are described below. If there is a question about these criteria, the investigator must consult with the appropriate sponsor representative and resolve any issues before enrolling a participant in the study. Waivers are not allowed.

For a discussion of the statistical considerations of participant selection, refer to Section 9.2, Sample Size Determination.

5.1. Inclusion Criteria

Each potential participant must satisfy all of the following criteria to be enrolled in the study:

- 1. Be a man or a woman at least 18 years of age (or the legal age of consent in the jurisdiction in which the study is taking place).
- 2. Have moderate to severe HS for at least 1 year (365 days) prior to the baseline visit as determined by the investigator through patient interview and/or review of the medical history.
- 3. Have HS lesions present in at least 2 distinct anatomic areas (examples include but are not limited to left and right axilla; or left axilla and left inguinocrural fold).
- 4. Had an inadequate response to an adequate course of appropriate oral antibiotics for treatment of HS (or demonstrated intolerance to, or had a contraindication to, oral antibiotics for treatment of their HS) in the investigator's opinion.
- 5. Have stable HS for at least 1 month (28 days) prior to the screening visit as determined by the investigator through patient interview and/or review of the medical history.
- 6. Have a total abscess and inflammatory nodule (AN) count of ≥ 3 at the screening and baseline visit.
- 7. Must agree to daily use (throughout the entirety of the study) of one of the following over-the-counter treatments to the body areas affected with HS lesions: either soap and water, or a topical antiseptic wash containing chlorhexidine gluconate, triclosan, or benzoyl peroxide, or a dilute bleach bath.

- 8. Before randomization, a woman must be either:
 - Not of childbearing potential: premenarchal; postmenopausal (>45 years of age with amenorrhea for at least 12 months or any age with amenorrhea for at least 6 months and a serum follicle-stimulating hormone (FSH) level >40 IU/L); permanently sterilized (eg, tubal occlusion, hysterectomy, bilateral salpingectomy); or otherwise be incapable of pregnancy.
 - Of childbearing potential and practicing a highly effective (failure rate of <1% per year when used consistently and correctly) method of birth control, prior to receiving study intervention, during the study and for at least 12 weeks after receiving the last administration of study intervention, consistent with local regulations regarding the use of birth control methods for participants participating in clinical studies: eg, established use of oral, injected or implanted hormonal methods of contraception; placement of an intrauterine device or intrauterine system; barrier methods: condom or occlusive cap (diaphragm or cervical/vault caps) plus spermicidal foam/gel/film/cream/suppository (if available in their locale); male partner sterilization (the vasectomized partner should be the sole partner for that participant); true abstinence (when this is in line with the preferred and usual lifestyle of the participant).

Note: If a female participant's childbearing potential changes after start of the study (eg, a woman who is not heterosexually active becomes active, a premenarchal woman experiences menarche), she must begin practicing a highly effective method of birth control, as described above.

- 9. A woman of childbearing potential must have a negative urine pregnancy test (β-human chorionic gonadotropin [β-hCG]) at screening and at Week 0 prior to administration of study intervention.
- 10. A woman must agree not to donate eggs (ova, oocytes) for the purposes of assisted reproduction during the study and for at least 12 weeks after receiving the last administration of study intervention.
- 11. A man who is sexually active with a woman of childbearing potential and who has not had a vasectomy must agree to use a barrier method of birth control (eg, either a condom [with spermicidal foam/gel/film/cream/suppository if available in their locale] or a partner with an occlusive cap [diaphragm or cervical/vault caps] plus spermicidal foam/gel/film/cream/suppository if available in their locale), during the study and for at least 12 weeks after receiving the last administration of study intervention.
- 12. All men must also agree to not donate sperm during the study and for at least 12 weeks after receiving the last administration of study intervention.

- 13. Are considered eligible according to the following tuberculosis (TB) screening criteria:
 - a. Have no history of latent or active TB before screening. An exception is made for participants who have a history of latent TB and
 - o are currently receiving treatment for latent TB,
 - o will initiate treatment for latent TB before the first administration of study intervention,
 - or have documentation of having completed appropriate treatment for latent TB within 5 years before the first administration of study intervention. It is the responsibility of the investigator to verify the adequacy of previous anti-TB treatment and provide appropriate documentation.
 - b. Have no signs or symptoms suggestive of active TB upon medical history and/or physical examination.
 - c. Have had no recent close contact with a person with active TB or, if there has been such contact, will be referred to a physician specializing in TB to undergo additional evaluation and, if warranted, receive appropriate treatment for latent TB before the first administration of study intervention.
 - d. Within 2 months before the first administration of study intervention, have a negative QuantiFERON®-TB test result, or have a newly identified positive QuantiFERON®-TB test result (see laboratory manual) in which active TB has been ruled out and for which appropriate treatment for latent TB has been initiated before the first administration of study intervention. Within 2 months before the first administration of study intervention, a negative tuberculin skin test, or a newly identified positive tuberculin skin test in which active TB has been ruled out and for which appropriate treatment for latent TB has been initiated before the first administration of study intervention, is additionally required if the QuantiFERON®-TB test is not approved/registered in that country or the tuberculin skin test is mandated by local health authorities.

NOTE: The QuantiFERON®-TB test and the tuberculin skin test are not required at screening for participants with a history of latent TB and ongoing treatment for latent TB or documentation of having completed adequate treatment as described above; participants with documentation of having completed adequate treatment as described above are not required to initiate additional treatment for latent TB.

- e. Have a chest radiograph (both posterior-anterior and lateral views, or per country regulations where applicable), taken within 3 months before the first administration of study intervention and read by a qualified radiologist, with no evidence of current, active TB or old, inactive TB.
- 14. Agree not to receive a live virus or live bacterial vaccination during the study, or within 12 weeks after the last administration of study intervention. For information on Bacille Calmette-Guérin (BCG) vaccination, see Inclusion Criterion 15.

- 15. Agree not to receive a BCG vaccination during the study, or within 12 months after the last administration of study intervention.
- 16. Have screening laboratory test results within the following parameters, if one or more of the laboratory parameters is out of range, a single retest of laboratory values is permitted:

a.	Hemoglobin	≥10 g/dL	(SI: \geq 100 mmol/L)
b.	White blood cells	$\geq 3.5 \times 10^{3}/\mu L$	(SI: ≥3.5 GI/L)
c.	Neutrophils	$\geq 1.5 \times 10^{3}/\mu L$	(SI: ≥1.5 GI/L)
d.	Platelets	$\geq 100 \text{ x } 10^3 / \mu L$	(SI: ≥ 100 GI/L)
e.	Serum creatinine	\leq 1.5 mg/dL	(SI: $\leq 137 \mu \text{mol/L}$)

- f. Aspartate aminotransferase $\leq 2 \times \text{upper limit of normal (ULN)}$
- g. Alanine aminotransferase $\leq 2 \times ULN$
- h. Alkaline phosphatase $\leq 2 \times ULN$
- 17. Be willing and able to adhere to the prohibitions and restrictions specified in this protocol.
- 18. Must sign an informed consent form (ICF) indicating that he or she understands the purpose of and procedures required for the study and is willing to participate in the study.

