Highly Effective Methods That Are User-Independent *Failure rate of* \leq *l*% *per year when used consistently and correctly.*

- Implantable progestogen-only hormone contraception associated with inhibition of ovulation^b
- Intrauterine device (IUD)
- Intrauterine hormone-releasing system (IUS)
- Bilateral tubal occlusion
- Vasectomized partner

(Vasectomized partner is a highly effective contraceptive method provided that the partner is the sole sexual partner of the woman of childbearing potential and the absence of sperm has been confirmed. If not, additional highly effective method of contraception should be used. Spermatogenesis cycle is approximately 74 days.)

USER-DEPENDENT

Highly Effective Methods That Are User-Dependent Failure rate of <1% per year when used consistently and correctly.

- Combined (estrogen- and progestogen-containing) hormonal contraception associated with inhibition of ovulation^b
 - oral
 - intravaginal
 - transdermal
 - injectable
- Progestogen-only hormone contraception associated with inhibition of ovulation^b
 - oral
 - injectable
- Sexual abstinence

(Sexual abstinence is considered a highly effective method only if defined as refraining from heterosexual intercourse during the entire period of risk associated with the study intervention. The reliability of sexual abstinence needs to be evaluated in relation to the duration of the study and the preferred and usual lifestyle of the participant.)

NOT ALLOWED AS SOLE METHOD OF CONTRACEPTION DURING THE STUDY (not considered to be highly effective - failure rate of >1% per year).

- Progestogen-only oral hormonal contraception where inhibition of ovulation is not the primary mode of action.
- Male or female condom with or without spermicide^c
- Cap, diaphragm, or sponge with spermicide
- A combination of male condom with either cap, diaphragm, or sponge with spermicide (double-barrier methods)^c
- Periodic abstinence (calendar, symptothermal, post-ovulation methods)
- Withdrawal (coitus-interruptus)
- Spermicides alone

- Lactational amenorrhea method (LAM)
- a) Typical use failure rates may differ from those when used consistently and correctly. Use should be consistent with local regulations regarding the use of contraceptive methods for participants in clinical studies.

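### Inclusion Criterion 8 and Appendix 7 contradict each other on barrier contraception and on who is postmenopausal, and no express rule says which governs

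*Protocol*

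**What the plan says.** **Contraception.** Protocol Section 5.1, Criterion 8, requires a woman of childbearing potential to use a highly effective method, defined by annual failure below 1%, and to follow local regulations for trial participants. Its list of alternative examples includes "barrier methods: condom or occlusive cap (diaphragm or cervical/vault caps) plus spermicidal foam/gel/film/cream/suppository". Appendix 7 (Section 10.7) has a list headed "NOT ALLOWED AS SOLE METHOD OF CONTRACEPTION DURING THE STUDY", explained as "not considered to be highly effective - failure rate of >1% per year". That list names "Male or female condom with or without spermicide" and "Cap, diaphragm, or sponge with spermicide", and also the double-barrier combination of a male condom with one of the latter devices.

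**Postmenopausal status.** Criterion 8 gives two routes: ">45 years of age with amenorrhea for at least 12 months", or "any age with amenorrhea for at least 6 months" together with FSH above 40 IU/L. Appendix 7 asks for 12 months without menses and no other medical explanation, at any age. It offers FSH as optional confirmation in women not on hormonal contraception or hormone replacement, and says that one value does not suffice before 12 months.

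**Which text governs.** Appendix 7 opens by sending the reader to Section 5.1 for contraceptive measures and cites Criterion 8. Section 5.3 also cites Criterion 8. Section 7.1 refers to Appendix 7 in connection with pregnancy. None of these says what to do when the two texts differ.

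**The concern.** Both texts are operative and bear on fetal exposure to study drug. A site that works from the eligibility criteria can accept a woman whose only contraception the appendix bars. It can also class as postmenopausal a woman whom the appendix still treats as able to conceive. The second error has the longer reach: the Schedule of Activities (footnote g) and Section 8.2.4 tie scheduled pregnancy tests to childbearing potential, so that classification removes both the contraception requirement and the testing.

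The sponsor evidently means the two sections to agree. The amendment summary reports that Appendix 7's post-dose contraception period was changed to match Criterion 8. These two differences remain in the current text.

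**Working it through.** The plan gives no figure to reproduce. The check sets the texts side by side and then counts what an exempted woman would miss.

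**1. Barrier methods.** Criterion 8's phrase can be read with spermicide attached to the cap only, or to both devices.

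| Sole method under Criterion 8 | Appendix 7 |
|---|---|
| Condom without spermicide | Barred |
| Condom with spermicide | Barred |
| Cap or diaphragm with spermicide | Barred |

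Combining the devices does not help, because double barrier is barred as well. One edge case: Criterion 8 asks for spermicide only where it is available. Appendix 7 does not name a cap without spermicide, but bars the same device with it.

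**2. Postmenopausal rule.** Inputs are the definitions in Criterion 8 and Appendix 7, assuming no alternative medical cause and a single FSH value.

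- Criterion 8 exempts if (age >45 and ≥12 months) or (≥6 months and FSH >40 IU/L).
- Appendix 7 exempts if ≥12 months.

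| Age | Amenorrhea | FSH >40 | Criterion 8 | Appendix 7 |
|---|---|---|---|---|
| ≤45 | 6 to <12 mo | yes | exempt | not exempt |
| ≤45 | 6 to <12 mo | no | not exempt | not exempt |
| ≤45 | ≥12 mo | yes | exempt | exempt |
| ≤45 | ≥12 mo | no | not exempt | exempt |
| >45 | 6 to <12 mo | yes | exempt | not exempt |
| >45 | 6 to <12 mo | no | not exempt | not exempt |
| >45 | ≥12 mo | yes | exempt | exempt |
| >45 | ≥12 mo | no | exempt | exempt |

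Criterion 8 is looser in two rows and Appendix 7 in one. With an alternative medical cause at ≥12 months, Criterion 8 could still exempt where Appendix 7 would not.

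**3. What a woman exempted under the 6-month route would miss.** The Schedule of Activities has a urine test at screening, at each of 10 dosing visits (Weeks 0, 4, 8, 12, 16, 20, 24, 28, 32, 36) and at Week 48 or early termination.

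- Maximum tests missed: 1 + 10 + 1 = 12.
- If she is tested at screening before the FSH result is known: 12 − 1 = 11.
- Contraception requirement lost, from first dose with all doses given: 36 + 12 = 48 weeks.

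Fewer doses give smaller figures. After one dose they are 1 + 1 + 1 = 3 tests (2 if tested at screening) and 12 weeks.

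**The case against.** The strongest reply is that the protocol does give direction. On contraception, Appendix 7 defers to Section 5.1 and Section 5.3 cites Criterion 8, so a reader who infers that the protocol is silent on where to look would be going too far. That stands. But these are cross-references, not a conflict rule, and they do not address the menopause definition. If they are taken as a ranking, they favor the looser text on barriers and on the 6-month route.

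Second, there are safeguards, and several work without anyone comparing the two sections. Criterion 8 itself demands failure below 1% and compliance with local regulations. Appendix 7 requires the method to meet local guidelines and suggests further evaluation when reproductive status is in doubt. Section 8 allows extra pregnancy tests that the investigator judges necessary or local rules require. Section 5 sends questions about the criteria to the sponsor before enrollment, and Criterion 17 requires adherence to the protocol's prohibitions. These reduce the risk. They do not reconcile the texts, and the last two help little where Criterion 8 appears to give a clear answer.

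Third, FSH is in neither the Schedule of Activities nor the Appendix 3 laboratory list, so the 6-month route depends on a test done outside the schedule. That probably limits its use, but the route remains open.

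Fourth, one might read the table as three discordant cells of eight and treat that as a measure of risk. It is not. The share depends on the grid: adding amenorrhea below 6 months, where the texts agree, makes it 3 of 12. No cell carries a frequency.

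**Conclusion.** The inconsistency is real and should be corrected. Criterion 8 offers as highly effective what Appendix 7 bars as sole contraception, and the two postmenopausal definitions differ in both directions.

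The textual mismatch is certain; its consequences are conditional. A site applying Criterion 8 could dose a woman relying only on a barred barrier method. It could also exempt a woman with 6 to <12 months of amenorrhea and FSH above 40 IU/L from contraception and from up to 12 scheduled urine tests, or up to 11 if she is tested at screening first. The maximum assumes all 10 doses and the final visit. The documents do not say how many women would be affected.

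Two stronger inferences are not supported. A reader might conclude that women on barrier methods would be dosed without pregnancy monitoring; they remain of childbearing potential and are tested at every dosing visit. A reader might also suppose that the trial's conclusions are at risk; sample size, power, type I error and endpoints are untouched.

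**What to change.** - **Contraception:** delete the barrier example from Criterion 8, or have Criterion 8 cite the Appendix 7 method list. Criterion 11, the barrier requirement for men, is separate and stays.
- **Menopause:** remove the 6-month FSH route and use one definition in both places: at least 12 months of amenorrhea without an alternative medical cause. As the conservative option, keep Criterion 8's FSH >40 IU/L requirement at age 45 or younger. In the table above, this rule exempts exactly the three rows that both texts already exempt, so it opens no new gap. Copying Appendix 7's definition alone would remove the conflict but drop the FSH requirement for younger women.

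**Cost:** a protocol clarification or an item in the next amendment, plus a check of women already enrolled on a barrier method alone or under the 6-month rule. The sample size and visit schedule do not change.

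The hemoglobin limit in Criterion 16a needs a separate editorial correction: 10 g/dL × 10 dL/L = 100 g/L, whereas the SI limit is printed in mmol/L.
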